Study protocol and statistical analysis plan

Evaluation of the Effectiveness of Extracorporeal Shockwave Therapy in Patients With Patellar Tendinopathy on Its Micromorphology

NCT number: NCT06102421

Date: October 4, 2023

(Date of approval of the project by the ethics committee)

Study design and description

This work is designed as a prospective cohort study, in which the effects of low-energy focused extracorporeal shock wave therapy (ESWT) in patients with patellar tendinopathy (PT) on its micromorphology will be monitored. It is estimated that at least 21 patients will participate. In addition, there will be a small control group of healthy tendons which will be monitored to observe magnitude of natural changes.

Patients in both groups will have same program. The research within one patient will last a total of 16 weeks from the initial to the final examination. Potential participants will be selected based on the recommendation of a specialist doctor and their suitability will be assessed according to the inclusion criteria. They will then be invited to an initial examination. This will include an objective examination by a physiotherapist, a subjective assessment by the patient and an ultrasonographic (USG) examination followed by a micromorphological analysis using special software.

Patient selection

Patient will be included in the study if they meet these inclusion criteria:

- is a recreational athlete performing intensive sport activity loading patellar tendon (running, jumping, strength training etc.) at least 3 days in a week for minimum of 1 hour per session,
- is in age between 18-40 years,
- has a patellar tendon pain, which limits (at least in part) the quality of normal daily or sports activities,
- has clinical manifestation of PT (pain and impaired function) confirmed by clinician,
- has symptoms only in one leg, the other one is asymptomatic.

Patient will not be included if:

- any contraindication for ESWT is present (according to International Society for Medical Shockwave Treatment (ISMST) consensus at https://shockwavetherapy.org),
- is aware of any symptomatic mechanical tendon damage in the past (e.g., partial or complete rupture in relation to the injury),
- neurological, oncological, or systemic disease (e.g., neuropathy, lupus or rheumatic arthritis) coexists,
- is/was already treated for PT elsewhere (e.g., platelet-rich plasma therapy, physiotherapy)
- is using blood thinning medications or statins.

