Initial and final examination

During the initial and final examinations, the several tasks to the patient will be performed. Firstly the anamnestic data will be collected, then the area of greatest pain will be localized by palpation.

Secondly, the patient will be asked to complete a validated Victorian Institute of Sports Assessment - Patella questionnaire, which assesses the subjectively perceived severity of the disease and partly its impact on the quality of normal daily or sports activities.

The patient's maximal pain will be assessed using a standardized numerical rating scale (NRS) of pain. The patient will be asked about the morning and maximum pain that could be caused by various factors.

Lastly, the ultrasonographic (US) examination of patient's AT in both legs will be performed. This examination is described in the following chapter.

Both, initial and final examinations in each patient will be performed by only one person (the investigator of the study). Follow-ups will be in the day of the last ESWT application (for NRS and VISA-P) and at 15 week (for all outcomes)

Ultrasonographic examination

US examination will be performed with a Mindray DC-70 machine with a linear probe type L12-3E with a frequency of 12 Hz in the preset "MSK" mode. The whole area of patellar tendon will be monitored from the apex patellae to the insertion site on the tibia by longitudinal and transverse imaging.

The values of anteroposterior tendon width at the anteroposterior widest point will be collected using the measuring instruments included in USG machine.

After that, the preset will be changed to the specific setting, and three pictures of each leg (symptomatic and asymptomatic) will be saved in long axis for subsequent micromorphological analysis using Spatial Frequency Analysis software (SFA). SFA is a non-invasive, specialized method which analyzes the US image. In particular, it analyzes the anisotropic B-mode speckle pattern arising from within a tissue type in the spatial frequency domain and is capable of detecting and comparing collagen fascicles organization, spacing, and density across various parameters. Mean of those three values will be used for statistical analysis.

ESWT application

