The low-energy focused ESWT will be applied using the BTL-6000 FSWT machine with piezoelectric generator and a coupling pad which modulates penetration depth to 0-35 mm. The setting is chosen based on ISMST guidelines (https://shockwavetherapy.org): Energy Flux Density (EFD) between 0.14-0.18 mJ/mm2 due to patient tolerance, frequency at 5 Hz. A total of 2000 shocks will be applied semi-statically to the most US defined pathological area in patellar tendon followed by 2000 shocks dynamically to the quadriceps muscle always using a contact gel. The set parameters will not change during the study and will remain the same for each patient.

Data analysis

The normality of the data distribution will be determined by calculating the Shapiro-Wilk p value. Independent t-tests (or Mann Whitney U tests for non-parametric) will be performed for each parameter to compare baseline values between symptomatic and asymptomatic limb for US and SFA parameters. In addition, paired t-tests (or Wilcoxon tests) will be performed for each parameter, evaluated in each group separately (symptomatic, asymptomatic) between baseline and final values. To reach effect size, Cohen's d will be calculated for paired t-tests and biserial rank correlation for non-parametric Wilcoxon test.

Intergroup statistical significance between baseline and follow-up values of morphological parameters will be evaluated using two-way ANOVA or non-parametric Kruskal-Wallis test. Statistical significance between time periods in VISA-P and NRS parameters will be evaluated using repeated measures ANOVA or non-parametric Friedman test with repeated measures.

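### No record of harms, missed ESWT sessions or reasons for stopping is named, and the planned VISA-P/NRS tests conventionally drop a patient with one missing score; a cheap improvement with modest gain

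*Combined protocol and SAP*

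**What the plan says.** **Assessments.** Under Initial and final examination, the listed tasks are history, palpation, VISA-P, NRS and ultrasound of both legs. The history item reads: "Firstly the anamnestic data will be collected, then the area of greatest pain will be localized by palpation". The NRS item reads: "The patient will be asked about the morning and maximum pain that could be caused by various factors". After baseline the schedule is: "Follow-ups will be in the day of the last ESWT application (for NRS and VISA-P) and at 15 week (for all outcomes".

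**Treatment.** ESWT application gives the device, energy, frequency and shock counts. Tolerance appears once, as the reason for the energy range: "Energy Flux Density (EFD) between 0.14-0.18 mJ/mm2 due to patient tolerance, frequency at 5 Hz". The number and spacing of sessions are not stated, nor is any step for a patient who cannot tolerate the setting.

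**Analysis.** Under Data analysis, the scores are handled thus: "Statistical significance between time periods in VISA-P and NRS parameters will be evaluated using repeated measures ANOVA or non-parametric Friedman test with repeated measures". The same section also says "paired t-tests (or Wilcoxon tests) will be performed for each parameter, evaluated in each group separately (symptomatic, asymptomatic) between baseline and final values". It gives no rule for missing scores.

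**Size.** Study design and description says: "It is estimated that at least 21 patients will participate". No dropout allowance is given.

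**The concern.** The plan expects tolerance to matter, yet names nowhere to write down that a patient had a reaction, missed a session or stopped, or why.

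Two things follow. First, short-lived reactions, and the reasons of those who do not come back, cannot be reliably reconstructed later, so a report that is silent on harms could not be read as showing none. Second, the middle VISA-P/NRS assessment is tied to the last treatment, so whether it is obtained may depend on how treatment went. A test that needs all three scores would then describe only patients with a full set, and readers could not see why the others were missing.

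The micromorphology aim is not wholly shielded. A patient who stops and does not return has no final scan. One who stops and returns is analysed as treated, with a lower dose that nobody recorded.

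**Working it through.** **1. What is and is not named.** Setting the examination tasks beside the treatment section, the nearest items to a harms or adherence record are the history, the NRS pain questions and the reference to tolerance. History at the final examination depends on recall and reaches only attenders. The NRS items ask about pain from any cause and do not separate a treatment reaction from the disease. The tolerance phrase explains a setting; it does not plan a record.

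**2. Time points.** Initial examination + last ESWT day + final examination = 3 for VISA-P and NRS. Ultrasound and spatial frequency measures have 2, the first and the last.

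**3. Inputs.** n = 21 is the plan's minimum. The number k of patients lacking only the middle score is assumed to be 1 to 4, because the documents give no rate.

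**4. Complete-case analysis.** The share lost is k/21. The rise in the standard error (SE) of a mean change is sqrt(21/(21 − k)) − 1; for k = 4, sqrt(21/17) − 1 = 11.1%. This describes the repeated measures ANOVA set, not Friedman.

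**5. Mixed model on all available scores.** Assume equal variances and a known correlation structure, with the k patients having baseline and final scores.
- Baseline-to-final: all 21 patients supply both scores, so the SE rise is 0%.
- Baseline-to-last-ESWT: SE rise = sqrt(1 + r·k/(21 − k)) − 1, where r is the residual variance of the middle score given the other two, divided by the variance of the change.
- Compound symmetry: r = (1 + 2ρ)/(2(1 + ρ)). For ρ = 0.3, 0.5, 0.7 this is 0.615, 0.667, 0.706.
- First-order autoregressive: r = (1 + ρ)/(2(1 + ρ²)). For the same ρ it is 0.596, 0.600, 0.570.
- So r lies between 0.570 and 0.706. For k = 4, sqrt(1 + 0.570 × 4/17) − 1 = 6.5% and sqrt(1 + 0.706 × 4/17) − 1 = 8.0%.

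| k missing of 21 | Share lost | Complete-case SE rise | Mixed model, baseline-to-final | Mixed model, baseline-to-last-ESWT |
|---|---|---|---|---|
| 1 | 4.8% | 2.5% | 0% | 1.4-1.7% |
| 2 | 9.5% | 5.1% | 0% | 3.0-3.6% |
| 3 | 14.3% | 8.0% | 0% | 4.6-5.7% |
| 4 | 19.0% | 11.1% | 0% | 6.5-8.0% |

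At k = 4 the model regains (11.1 − 8.0)/11.1 = 28% to (11.1 − 6.5)/11.1 = 41% of the loss in the second contrast.

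**6. If the early stoppers do not return.** They then have a baseline score only, and the 0% no longer holds. Under compound symmetry r becomes (1 + ρ)/2, which is 0.65 to 0.85 for ρ = 0.3 to 0.7. For k = 4 the SE rise in either contrast is sqrt(1 + 0.65 × 4/17) − 1 = 7.4% to sqrt(1 + 0.85 × 4/17) − 1 = 9.5%, little better than 11.1%. The paired micromorphology tests lose the same k patients, with the complete-case rise in step 4.

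**7. What a harms record could show.** If all 21 are asked and none reports a given harm, the exact upper limit for its rate is 1 − 0.05^(1/21) = 13.3% (one-sided 95%) or 1 − 0.025^(1/21) = 16.1% (two-sided). A harm with an assumed true rate of 5%, 10% or 20% would occur at least once with probability 1 − (1 − p)^21 = 66%, 89% or 99%.

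**The case against.** **Nothing says that patients will be dropped.** Correct. The plan is silent on missing scores; the exclusion is how the named tests conventionally work, not a stated rule.

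**An early stopper also has a last application.** True, and a score could be taken that day. But it may not be known at the time to be the last, and it would fall at a different point from other patients' middle score. How often this would happen is unknown.

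**The effect is small and lies outside the title aim.** For 1 or 2 losses it is 2.5-5.1% on the standard error, and the mixed model regains only part of that for the last-ESWT contrast. The paired tests are planned for every parameter and, if they include VISA-P/NRS, already keep a returning patient; the split by limb leaves this unclear. This stands and limits the weight of the analysis part.

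**The plan makes no safety claim.** Also true. The harms figures show what a record would allow, not an error in a stated analysis.

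Three stronger readings are tempting. A reader might infer that nothing about harms could be captured; the history and pain items contradict that. A reader might infer that micromorphology is untouched because its tests skip the middle visit; those tests still need a final scan, and the dose behind it would be unrecorded. A reader might infer that the VISA-P/NRS results are biased; the documents give no dropout rate and no basis for a size or direction.

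**Conclusion.** The point holds as a cheap improvement. The plan names no record of harms, missed sessions or reasons for stopping, and its three-time-point tests for VISA-P and NRS conventionally need complete rows at a visit that early stoppers are the most likely to miss.

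The precision at stake is modest, and the loss counts behind it are assumed. The full recovery for baseline-to-final depends on early stoppers attending the final examination, and the partial recovery for the last-ESWT contrast on correlations of 0.3 to 0.7. For micromorphology the issue is attendance and unrecorded dose, not the middle visit. The checklist is the more time-critical part, because it cannot be filled in reliably afterwards.

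**What to change.** 1. **Analysis.** Analyse VISA-P and NRS with a mixed model with time as a three-level factor, using all available scores. Keep Friedman as a sensitivity analysis.
2. **Early stoppers.** Keep the end-of-treatment assessment on the last ESWT day for completers. For those who stop early, take NRS and VISA-P when their last session had been planned, and invite them to the final examination including ultrasound. This requires the number and spacing of sessions to be fixed in the protocol.
3. **Record.** At each ESWT session already planned, and at the final examination, complete a short checklist: pain limiting treatment, haematoma or skin change, new tendon injury, session missed and why. Report harms, sessions received and reasons for stopping for everyone who had at least one session.

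**Cost.** A one-page form and a few questionnaires on non-treatment days; no extra patients or equipment. The mixed model assumes that scores are missing at random and that residuals are approximately normal.

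### The baseline comparison of symptomatic and asymptomatic limbs applies independent-samples tests to two legs of the same patient

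*Combined protocol and SAP*

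**What the plan says.** Under Patient selection, a patient qualifies only if he or she "has symptoms only in one leg, the other one is asymptomatic". Under Ultrasonographic examination, "three pictures of each leg (symptomatic and asymptomatic) will be saved in long axis", and the three readings are averaged, so the analysis has one value per leg per patient. The Data analysis section then sets three comparisons that matter here:

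- Baseline, between limbs: "Independent t-tests (or Mann Whitney U tests for non-parametric) will be performed for each parameter to compare baseline values between symptomatic and asymptomatic limb".
- Over time, within limb: "paired t-tests (or Wilcoxon tests) will be performed for each parameter, evaluated in each group separately (symptomatic, asymptomatic) between baseline and final values".
- Between groups: "Intergroup statistical significance between baseline and follow-up values of morphological parameters will be evaluated using two-way ANOVA or non-parametric Kruskal-Wallis test".

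A repeated-measures method is named only for VISA-P and NRS. Separately, Study design and description says that "there will be a small control group of healthy tendons which will be monitored to observe magnitude of natural changes". It does not say whose tendons these are, and no test in the Data analysis section names them.

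**The concern.** The independent t-test and the Mann-Whitney U test assume unrelated units. On the natural reading, the two limbs compared at baseline are the two legs of one person, who shares age, body size, training load and the examiner across both measurements. The plan recognises pairing over time but not between legs.

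What is at stake is precision. The independent test leaves the between-leg covariance out of the variance of the mean side difference. With a positive correlation, which is plausible but not documented, the p-value is too large and a real side difference can be missed. With a negative correlation the error runs the other way.

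The intergroup sentence names no patient term. If its groups are the symptomatic and asymptomatic limbs, as the preceding paragraph of the section labels them, the same fault reaches the comparison of change between limbs. That comparison lies closer to the study's aim than the baseline one.

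**Working it through.** **Inputs.** The number of pairs comes from Study design and description: "It is estimated that at least 21 patients will participate". The plan gives no significance level, power, effect size, SD or between-leg correlation, so there is no derivation of 21 to reproduce, and the point does not depend on one. Assumed here: 21 complete pairs, two-sided 5%, bivariate normal values, and a range of correlations ρ, SD ratios and side differences.

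**Standard error.** With limb SDs s1 and s2, the true variance of the mean difference is (s1² + s2² − 2ρ·s1·s2)/n. The independent test uses (s1² + s2²)/n. The ratio of assumed to true standard error is therefore

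1/√(1 − 2ρ·s1·s2/(s1² + s2²)).

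- Equal SDs: 1/√(1 − ρ), which gives 1/√0.7 = 1.20, 1/√0.5 = 1.41 and 1/√0.3 = 1.83 for ρ = 0.3, 0.5 and 0.7.
- SD ratio 2:1: 2·2·1/(4 + 1) = 0.8, so 1/√(1 − 0.8ρ), which gives 1/√0.76 = 1.15, 1/√0.60 = 1.29 and 1/√0.44 = 1.51.

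**Type I error and power.** The independent test has 40 df and the paired test 20 df. Paired power comes from the noncentral t distribution. For example, at ρ = 0.5 and 0.5 SD the noncentrality is 0.5/√(2 × 0.5/21) = 2.29, giving power 0.59. For ρ of 0 and above, the independent test's rejection rates were computed numerically and agreed with simulation (200,000 datasets per setting) within 0.003. The row for ρ = −0.2 is from simulation (400,000 datasets). Equal SDs:

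| ρ | SE ratio | Type I error, independent | Power at 0.5 SD, independent v paired | Power at 1.0 SD, independent v paired |
|---|---|---|---|---|
| −0.2 | 0.91 | 7.3% | 0.37 v 0.29 | – |
| 0 | 1.00 | about 5% | 0.35 v 0.34 | – |
| 0.3 | 1.20 | 2.1% | 0.33 v 0.45 | 0.92 v 0.96 |
| 0.5 | 1.41 | 0.7% | 0.30 v 0.59 | 0.95 v 0.99 |
| 0.7 | 1.83 | 0.1% | 0.27 v 0.80 | 0.98 v 1.00 |

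The higher power of the independent test at ρ = −0.2 is bought with an inflated type I error. The paired test holds 5% throughout.

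With a 2:1 SD ratio (differences in root-mean-square SD) the loss is smaller. For ρ = 0.3, 0.5 and 0.7, type I error is 2.8%, 1.5% and 0.55%, and power at 0.5 SD is 0.34 v 0.42, 0.32 v 0.51 and 0.30 v 0.64.

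**Rank tests.** At ρ = 0.5 with equal SDs, Mann-Whitney rejects 0.8 to 0.9% of the time under no difference. Its power at 0.5 SD is 0.28, against 0.55 for the signed-rank test.

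**Intergroup analysis, if the groups are the two limbs.** If time is handled as repeated but the legs as unrelated, the equal-SD table applies, with ρ read as the correlation between the two legs' changes and the difference in SDs of change. A wider scenario was simulated with between-leg correlation 0.5, over-time correlation 0.7, cross-correlation equal to their product, and an extra change of 0.5 SD in one limb. Power for the limb-by-time contrast was:

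- 0.03 for a two-way ANOVA on 21 × 2 × 2 = 84 values treated as independent;
- 0.54 when time is repeated but the legs are unrelated;
- 0.80 for a paired test of the within-patient difference in change.

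Of the total loss, 0.80 − 0.03 = 0.77, ignoring the legs' pairing accounts for 0.80 − 0.54 = 0.26 and ignoring time for 0.54 − 0.03 = 0.51. Under no effect, Kruskal-Wallis on the four limb-by-time cells rejects 0.7% of the time, again from both sources together.

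**The case against.** The strongest defence concerns the intergroup sentence. The plan uses the word group in two senses: the Data analysis section attaches it to the two limbs, whereas the design section, straight after introducing the healthy-tendon controls, says that patients in the two groups follow an identical programme. That suggests the controls may be separate people, and Kruskal-Wallis, usually chosen for three or more groups, is compatible with a third group. Two-way ANOVA is also a loose label that does not exclude a repeated-measures version. This stands to the extent that the intergroup part is conditional on what the groups are. It does not help the baseline sentence, which speaks of symptomatic and asymptomatic limbs, the terms used elsewhere for a patient's own two legs. If control tendons were pooled with the asymptomatic legs, the data would still be partly paired and the independent test still wrong.

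The second defence is that little harm follows. The baseline comparison describes diseased against healthy limbs and does not estimate the effect of treatment. The tests of change within each limb are correctly paired. Under positive correlation a significant result remains credible, and at 1 SD the power loss is at most 0.96 − 0.92 = 0.04 for the correlations shown. All of this is true, and it limits the severity. The test still does not match the design, and a finding of no side difference from it could not be trusted.

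**Conclusion.** The baseline between-limb test is wrong as written. Its standard error and p-value hold only at zero between-leg correlation, a condition the plan neither states nor supports. For moderate differences (0.5 SD) and equal SDs, the cost in power runs from 0.45 − 0.33 = 0.12 at a correlation of 0.3 to 0.80 − 0.27 = 0.53 at 0.7. It is smaller with unequal SDs and small near 1 SD. These sizes rest on assumed correlations, SDs, effect sizes and a 5% level, with 21 complete pairs. The point estimate is unaffected.

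The intergroup analysis has the same defect if its groups are the two limbs. The documents leave that open, so the first need there is clarification. This should be corrected before analysis, but it does not undermine the study as a whole.

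**What to change.** Replace the baseline sentence with wording such as:

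> Baseline US and SFA values of the two limbs of each patient will be compared with a paired t-test on the within-patient difference, or a Wilcoxon signed-rank test if those differences are clearly non-normal.

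In the intergroup sentence, state which groups are meant. If they are the two limbs, specify for example:

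> The change from baseline to follow-up will be compared between limbs with a paired t-test (or Wilcoxon signed-rank test) on the within-patient difference in change.

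A mixed model with patient as a random effect, or a two-way ANOVA with both limb and time as repeated factors, would also respect the pairing.

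State who the healthy-tendon controls are. If they are separate people, compare them in a separate analysis and do not pool them with the contralateral limbs.

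The cost is two sentences of analysis wording and one of clarification. Both legs are already measured at the initial and final examinations, so no new data are needed. Should the legs prove uncorrelated, the paired test gives up almost nothing (power 0.34 against 0.35 at 0.5 SD).

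### The intergroup test of morphological change is written as an unpaired two-way ANOVA or Kruskal-Wallis test on values repeated within patients, and its groups are not named

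*Combined protocol and SAP*

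**What the plan says.** The comparison of morphological change between groups rests on one sentence in the Data analysis section: "Intergroup statistical significance between baseline and follow-up values of morphological parameters will be evaluated using two-way ANOVA or non-parametric Kruskal-Wallis test". It does not name the two factors, the effect of interest, or any within-person structure.

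The sentence after it does specify repeated measures, but only for the clinical scores: "Statistical significance between time periods in VISA-P and NRS parameters will be evaluated using repeated measures ANOVA or non-parametric Friedman test with repeated measures". Earlier in the section, baseline limb values are to be compared by independent-samples tests, although the two limbs belong to the same person. Paired tests over time are planned for each limb, "evaluated in each group separately (symptomatic, asymptomatic) between baseline and final values".

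The Ultrasonographic examination section states that "three pictures of each leg (symptomatic and asymptomatic) will be saved in long axis", and the three readings are averaged. Morphology is taken at the initial examination and at week 15.

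The word group has two uses. In the Data analysis section it means the two limbs. In Study design and description it means patients and "a small control group of healthy tendons which will be monitored to observe magnitude of natural changes", followed by "Patients in both groups will have same program". The size of the control group is not given.

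**The concern.** This is the only planned test that sets change in the symptomatic tendon against change in a comparator. The per-limb paired tests respect pairing over time but cannot show that one limb changed more than the other. The sentence therefore bears most directly on whether shockwave therapy alters micromorphology.

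Three things could go wrong:

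- An ordinary two-way ANOVA takes its error term from independent observations. With positively correlated repeats, that error is too large for the group-by-time interaction, and power is lost.
- Kruskal-Wallis assumes independent samples and has no interaction term. On raw values in the four cells, a baseline difference between limbs is enough for significance. On change scores it responds to differential change but ignores the pairing of limbs.
- If the groups are the limbs, the control group has no assigned analysis. If they are patients and controls, time is still a within-person factor that the plan does not declare.

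**Working it through.** **Inputs.** From the documents: at least 21 patients, two limbs each, two examinations for morphology. Assumed, because the documents give none: two-sided 5% level, SD 1 in every cell, the correlations, the effect sizes and the number of controls. The plan states no power figure for this test, so there is none to reproduce.

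**Limb reading: standard errors.** Let D be a patient's change in the symptomatic limb minus change in the asymptomatic limb.

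- Equal correlation ρ among the four values: Var(D) = 4(1 − ρ).
- Product structure, with correlation r over time and s between limbs: Var(D) = 4(1 − r)(1 − s).
- The plain ANOVA in effect uses 4, whatever the correlation.

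With n = 21, the plain standard error is √(4/21) = 0.436. The true one is √(4 × 0.5/21) = 0.309 at ρ = 0.5, and √(4 × 0.3 × 0.5/21) = 0.169 at r = 0.7, s = 0.5.

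The plain test (80 df) needs an observed difference of about 1.990 × 0.436 = 0.87 SD for significance. The one-sample test on D (20 df) needs about 2.086 × 0.309 = 0.64 SD in the first case and 2.086 × 0.169 = 0.35 SD in the second.

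**Limb reading: simulation** (multivariate normal, 40,000 runs per setting)

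| Correlation | True difference in change | Plain interaction, power | One-sample test on D, power | Plain interaction, type I error |
|---|---|---|---|---|
| equal, 0 | 0.8 SD | 0.44 | 0.42 | 4.8% |
| equal, 0.3 | 0.8 SD | 0.43 | 0.55 | 2.1% |
| equal, 0.5 | 0.8 SD | 0.42 | 0.69 | 0.7% |
| equal, 0.7 | 0.8 SD | 0.41 | 0.89 | 0.1% |
| time 0.7, limb 0.5 | 0.5 SD | 0.03 | 0.80 | below 0.01% |

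The test on D holds its error at about 5% throughout.

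**Kruskal-Wallis** (4,000 runs per setting)

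- Raw limb-by-time cells, no change in any tendon, limbs differing by a constant 0.8 SD: rejects in about 85 to 90% (equal correlation 0 to 0.7) or 80% (time 0.7, limb 0.5). For a 0.5 SD limb difference it rejects in 25 to 42%.
- Limb change scores, time 0.7 and limb 0.5, true difference 0.5 SD: type I error 0.8% and power 0.51, against 5.1% and 0.78 for the signed-rank test on D. If the two limbs' changes are uncorrelated (equal correlation 0.7), there is little between them: 0.51 against 0.49.

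**Patients against controls** (21 patients, 5 to 15 controls, difference in change 0.8 SD, 20,000 runs)

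- Time correlation 0.5: plain interaction 0.13 to 0.34, two-sample test on change 0.34 to 0.64.
- Time correlation 0.7: 0.08 to 0.30 against 0.51 to 0.84.
- Time correlation 0: no loss.
- Precision at time correlation 0.5, where a change has SD √(2 × 0.5) = 1: the 95% CI half-width is 2.064 × √(1/21 + 1/5) = 1.0 SD with 5 controls and 2.032 × √(1/21 + 1/15) = 0.7 SD with 15.

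**Equivalence of the proposed analyses.** On one simulated dataset (time 0.7, limb 0.5), the squared one-sample t, the fully within-patient repeated-measures F(1,20), and the squared z from a mixed model with patient, patient-by-limb and patient-by-time effects were all 20.17. Without patient-by-time, the mixed model gave z = 2.56 instead of 4.49. The plain ANOVA gave F(1,80) = 2.11, p = 0.15.

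**The case against.** The plan is silent on the error term; it does not state an unpaired one. It mentions baseline and follow-up, so time is presumably a factor, and a repeated-measures two-way ANOVA may be what is meant. That is possible. But the next sentence names repeated measures for other outcomes, and the baseline limb comparison uses independent-samples tests, so the unpaired reading is the natural one. The charitable reading also does not rescue Kruskal-Wallis.

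The limbs are the likelier meaning of group, since the preceding sentences label them so. This is fair, but it leaves the controls without an analysis. They may be intended as descriptive only, and with intervals of ±0.7 to ±1.0 SD a formal comparison would be imprecise. If so, the plan should say it.

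The ANOVA figures take the group-by-time interaction as the target, which the plan does not state. This stands, and it limits the reassurance that the error is conservative. With patients against controls, the plain ANOVA group main effect rejects a true null in about 11% of trials at time correlation 0.5 and 13% at 0.7. For the limb main effect the rate is 7% with time 0.7 and limb 0.3, and 3% with time 0.7 and limb 0.5.

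The Kruskal-Wallis false positive needs several conditions: non-normal data, raw cells and a baseline limb difference. None is far-fetched, and the plan itself sets out to test for a baseline limb difference.

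**Conclusion.** The concern holds. As written, the plan's only test of differential morphological change does not account for repeats within patients, its rank fallback can answer a different question, and its groups are not named.

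The power loss for the interaction runs from none at zero correlation to 0.03 against 0.80 at time correlation 0.7 and limb correlation 0.5. All sizes depend on assumed correlations, effects and control numbers. The direction does not: under the positive correlations considered, the plain interaction is conservative and does not itself create false positives. The risk of a misleading positive comes from Kruskal-Wallis on raw cells. The sentence should be corrected before the morphological data are analysed.

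**What to change.** Replace the intergroup sentence with two named contrasts:

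- **Limb contrast.** For each morphological parameter, compute per patient (final − baseline) in the symptomatic limb minus (final − baseline) in the asymptomatic limb. Test it with a one-sample t-test and report a 95% CI. Use the Wilcoxon signed-rank test on the same difference if those differences are clearly non-normal. If a model is preferred, use a repeated-measures ANOVA with limb and time both within patient, or a mixed model with patient, patient-by-limb and patient-by-time random effects.
- **Control contrast.** Compare change in the symptomatic tendon with change in the healthy control tendons by a two-sample test on change scores, with a 95% CI. Use one value per control person, or a person effect if both tendons are used. If the controls are meant to be descriptive only, state that and report their mean change with its 95% CI.

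Delete Kruskal-Wallis, assess normality on these differences and change scores, and use the contrast names in place of intergroup. State before analysis which option applies wherever a choice is left open. The cost is a few sentences: the measurements, visits and software are unchanged.
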